COVER PAGE

Study Title: Addressing Health Disparities in Childhood Obesity, One Summer at a Time

Clinical Trials Registration Number: NCT03595332

Date of document: April 15, 2018

Study Protocol

Background

Childhood obesity is one of the most urgent health challenges of our time. Obesity rates of Native American and Hispanic children are far higher than national averages, placing these children at high risk for early mortality, cardiovascular and metabolic conditions including diabetes, depression and overall poor quality of life.¹⁻³ By the 5th grade, approximately 50% of Hispanic and Native children are already overweight, and Native children have type 2 diabetes rates 9 times higher than non-Hispanic Whites.⁴ In our area, obesity rates are highly concentrated: most obese and overweight children are enrolled in 4 of the 10 elementary schools, which include primarily underserved Hispanic and Native American children.

Recent research has further demonstrated that the 'obesity gap' facing minority students is largely due to summer weight gain.⁵⁻⁹ Based on local data, it was confirmed that children in our school district were much more likely to worsen their weight-related health status during the summer than during the schoolyear. However, statewide, only 22% of children participate in summer activities, despite 65% of parents expressing interest.¹⁰ Finally, ages 7 to 11 have been found in national data to see a sharp increase in obesity rates.¹¹ Indeed, locally in 2015, approximately 20% of 7 year-olds are overweight or obese, but 35% of 11-year olds. Thus, we know which populations are at highest risk, at what developmental age changes occur most rapidly (ages 7-11) and that interventions are most needed in the summer, but that this need is not being met.

A modest amount of research has evaluated summer programming, but almost none among Native Americans/Hispanics. In the early 2000s, the CDC developed a 'Summer Scorecard' intervention,¹² a partnership with local businesses to provide children with a 'scorecard' of subsidized or free local activities. The VSS has not been tested among Hispanic and Native American children. Therefore, this study assessed the effectiveness of the VSS among children ages 5-13 in the 4 highest risk schools in the Flagstaff area. Outcomes included body composition (BMI) percentile score, reported physical activity and self-efficacy using survey instruments previously developed and tested by the CDC.

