Sample Size calculations: The estimated sample size needed to have sufficient power to detect a moderate effect size (using a Cohen's d of 0.3 as the reference) is 240 children, or 120 per arm. Based on our preliminary data, for each academic year, the average BMI change ranges from 0.35 to 0.55 units, with a standard deviation that varies across ethnic groups and years from 0.80

to 1.00. An example of an effect between two groups or time points that would match a Cohen's d of 0.3 would be one group in which the children on average increases their BMI by 0.5 units, and another group where participants increase their BMI by 0.2 units (0.3 unit difference), with standard deviations of 1.0. These effects (BMI difference of 0.3kgm^2) are just above the mean weighted effect size reported in the most comprehensive and recent meta-analysis on childhood obesity studies of 0.30kg/m^2 .^{9,10} With a two-tailed test and alpha level of 0.05, a sample size of 80 children per arm (a retention rate of 67%) would result in an associated statistical power $\geq 80\%$ to detect intervention effects between arms from one time point to the next. With very similar parameters and sample sizes, prior research has indicated that based on simulation studies,¹⁷ these parameters demonstrated excellent power ($\geq 80\%$) in detecting these size differences.

Institutional Review Board:

All protocol activities were approved by the Institutional Review Board of Northern Arizona University (protocol #1193689) and the Flagstaff Unified School District. Parental consent forms and children assent were attained for each participant.

References:

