COVER PAGE

Study Title: Addressing Health Disparities in Childhood Obesity, One Summer at a Time

Clinical Trials Registration Number: NCT03595332

Date of document: July 14, 2022

Statistical Analysis Plan

The proposed statistical analyses for the current study includes a nested regression model utilizing Generalized Estimating Equations with an exchangeable working correlation matrix to account for the nested data structure of children within schools and families. For all variables, 95% Confidence intervals will be reported (for b in models with a linear response variable and Odds Ratios for models with an ordinal logistic response variable) and a significance level of $p=0.05$ will be used to test hypotheses.

For the primary analysis, we propose to test the difference in Body Mass Index (BMI) Percentile-scores for age and sex based on Centers for Disease Control and Prevention (CDC) criteria from Baseline to 10-weeks using GEE models with a linear response variable. We will test whether the difference is significantly different from zero, adjusting for age (included as a covariate) and sex and ethnicity (included as factors). We will also test whether the immediate intervention group was significantly different from the delayed intervention group by including a variable denoting immediate vs delayed group membership. We will test the null hypothesis that participants in the intervention did not significantly change their BMI Percentile-score.

For the second primary analysis, we will test whether the BMI Percentile from baseline to 10-weeks was significantly different from zero among the highest-risk children, defined as those participants with a baseline BMI Percentile score equal to or greater than the 85th percentile as considered by the Centers for Disease Control and Prevention. GEE models will be used restricting the sample to children with overweight at baseline.

For the first secondary analysis, we propose to test the difference in Body Mass Index Percentile-score from Baseline to 1-year follow-up using GEE models with a linear response variable. We will test whether the difference is significantly different from zero, adjusting for age (included as a covariate) and sex and ethnicity (included as factors). We will test the null hypothesis that participants in the intervention did not significantly change their BMI Percentile-score.

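### Two nested tests are both labelled primary at 0.05, with an immediate-vs-delayed test of unstated status beside them, and no rule says which success supports a primary claim

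*SAP*

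**What the plan says.** The opening paragraph of the SAP sets one threshold for everything: "a significance level of $p=0.05$ will be used to test hypotheses".

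The primary analysis begins: "For the primary analysis, we propose to test the difference in Body Mass Index (BMI) Percentile-scores for age and sex". It tests the change from baseline to 10 weeks against zero. In the same paragraph the SAP adds: "We will also test whether the immediate intervention group was significantly different from the delayed intervention group". It does not say whether that comparison is part of the primary decision.

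The next paragraph begins: "For the second primary analysis, we will test whether the BMI Percentile from baseline to 10-weeks was significantly different from zero". It applies the same test, at the same time point, to children at or above the 85th percentile at baseline. This sample is a subset of the first.

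The 1-year BMI-percentile change and the self-efficacy score follow as secondary analyses. The subgroup analysis therefore stands at primary level.

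The Sample Size calculations section of the protocol bases its power statement on a different contrast: the trial is powered "to detect intervention effects between arms from one time point to the next". Neither document mentions a conditional testing order, a split of alpha, or a requirement that both primary tests succeed.

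**The concern.** Two or three tests at 0.05 could each be read as answering the primary question, and the plan does not say which one does. Nothing in it prevents a primary claim that rests on the subgroup alone when the full-sample test is null. If that is allowed, the chance of a false primary claim exceeds 5%. If both change tests had to succeed, it would not. The missing rule decides which case applies.

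**Working it through.** **Inputs**
- Level per test: 0.05 (SAP, opening paragraph). Two-sided, as in the protocol's sample size section, so the critical value is 1.960.
- Share f of children at or above the 85th percentile: not given for the trial. Assumed 20% and 35% (local figures for 7- and 11-year-olds, protocol Background), 50% (the Background figure for Hispanic and Native 5th graders), and 60% as a stress value, because the Background says overweight is concentrated in the schools studied.
- Children: 2 × 80 = 160 (protocol, after dropout). Four schools: "this study assessed the effectiveness of the VSS among children ages 5-13 in the 4 highest risk schools in the Flagstaff area". Equal schools of 40 are assumed.
- School correlation ρ: not given; assumed 0 to 0.10.
- Ratio s of the subgroup's SD of change to that of other children: not given; assumed 0.5 to 1.25.
- Null: zero mean change, with each test holding exactly 5%.

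**The plan's own figure.** The documents state no family-wise error, so there is none to reproduce. The protocol's power figure does not enter this calculation.

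**Step 1: independent children, equal variances.** The full-sample mean contains the subgroup mean with weight f, so the two test statistics have correlation r = √f. Then P(either) = 1 − P(|Z1| < 1.960 and |Z2| < 1.960), from the bivariate normal, and P(both) = 0.10 − P(either).

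| f | r | either | both |
|---|---|---|---|
| 20% | 0.447 | 9.21% | 0.79% |
| 35% | 0.592 | 8.78% | 1.22% |
| 50% | 0.707 | 8.31% | 1.69% |
| 60% | 0.775 | 7.96% | 2.04% |

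Two independent tests would give 1 − 0.95² = 9.75%; the ceiling is 10%.

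**Step 2: clustering in schools.** r = √{f(1 + 39ρ) / (1 + (40f − 1)ρ)}. For f = 20, 35, 50 and 60%:
- ρ = 0.05: r = 0.661, 0.791, 0.870, 0.907; either = 8.52, 7.86, 7.31, 6.96%.
- ρ = 0.10: r = 0.759, 0.864, 0.919, 0.944; either = 8.05, 7.36, 6.84, 6.54%.

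**Step 3: unequal SDs, no clustering.** r = s√f / √(fs² + 1 − f). For the same f:
- s = 0.5: r = 0.243, 0.344, 0.447, 0.522; either = 9.59, 9.44, 9.21, 9.01%.
- s = 1.25: r = 0.530, 0.676, 0.781, 0.837; either = 8.99, 8.45, 7.92, 7.56%.

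Steps 1 to 3 span 6.54% to 9.59%.

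**Step 4: clustering and unequal SDs together.** Let the school effect in the subgroup be λ times that in other children (λ = 1 or s), and L = fλ + 1 − f. Then:
- Var(sub) = λ²ρ/4 + s²(1 − ρ)/(160f)
- Var(full) = L²ρ/4 + (1 − ρ)(fs² + 1 − f)/160
- Cov = λLρ/4 + s²(1 − ρ)/160

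At ρ = 0.10 and f = 60%, λ = 1 with s = 0.5 gives r = 0.0264/√(0.0273 × 0.0281) = 0.953 and 6.4%. With λ = s = 1.25, r = 0.0447/√(0.0537 × 0.0406) = 0.958 and 6.3%. The low end of 6.5% is therefore approximate.

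**Step 5: immediate-vs-delayed test counted too** (independent children, equal variances, equal arms; f = 20, 35, 50%).
- Change tests pooled over arms: the between-arm contrast is independent of both, so the error is 1 − 0.95 × (1 − either) = 13.75, 13.34, 12.89%.
- Change tests in the immediate arm only: the between-arm statistic has correlation √(1/2) with the full-sample test and √(f/2) with the subgroup test. Simulation gives 12.3, 11.8, 11.4%.

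The SAP does not say which applies.

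**Step 6: what a split does.** At 0.025 for each of two tests, the Step 1 error is 4.71, 4.51 and 4.28% for f = 20, 35 and 50%. At 0.0167 for each of three tests it is 4.5-4.8% (pooled) or 4.1-4.3% (immediate arm only). A test with 80% power at 0.05 has expected statistic 1.960 + 0.842 = 2.802. At 0.025 the critical value is 2.241 and power is Φ(0.560) = 71%. At 0.0167 it is 2.394 and power is Φ(0.408) = 66%. The 80% is a reference level only, not a statement about this trial's power.

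**The case against.** The inflation is conditional. A reader might infer that the plan intends to claim success on the subgroup alone, or that the trial's error rate is 8-9%. No sentence says that one success suffices, so neither follows. The documents also claim no family-wise control, so this is unaddressed multiplicity and not a misstated figure. This objection limits the conclusion to the missing rule and its possible consequences.

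It can be said that the labels already imply an order. They give an order of listing, but nothing makes the subgroup test depend on the full-sample result, and the SAP has a separate secondary tier.

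The percentages rest on assumed shares, correlations and SD ratios, and on each test holding its size. That last condition may fail. The GEE is meant "to account for the nested data structure of children within schools and families", but the SAP names neither the clustering unit for the variance nor a small-sample correction. With 4 schools of 40 as clusters, an uncorrected sandwich variance and a normal reference, simulation rejects at about 19% per test and about 27-31% for either. A reader might take those as this plan's error rates; the SAP does not specify that variance, so it is a separate question.

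Zero mean change is also not the same as no intervention effect. Summer drift, or regression to the mean in a subgroup selected on high baseline values, could produce a significant change however alpha is allocated. This stands, and the figures do not cover it.

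Finally, a prospective fix may no longer be available. The protocol of April 2018 is largely in the past tense, the Appendix A scorecard closes on a Sunday 6 August (within 2012-2022, only 2017 fits), and the SAP is dated July 2022. A reader might infer that the SAP was written with results in hand. The dates make that plausible but do not prove it: the SAP speaks of proposed analyses, and the scorecard may come from an earlier season.

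**Conclusion.** The concern holds as a gap in the decision rule. It is certain that two nested tests are labelled primary at 0.05 with no rule linking them, and that the immediate-vs-delayed test has no stated place.

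The size is conditional on either change test being sufficient, zero mean change and exact 5% size per test:
- about 8-9% for shares of 20-50% with independent children and equal variances;
- roughly 6.5-10% over school correlations up to 0.10, SD ratios of 0.5-1.25 and shares up to 60%;
- about 11-14% if the immediate-vs-delayed test also counts (independent children, equal variances, shares of 20-50%).

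If both change tests had to succeed, the error under zero mean change would be below 5% (0.8-1.7% in the base case for shares of 20-50%). Confidence is high that the rule is missing and moderate in the percentages. The gap should be fixed, but it does not invalidate the trial.

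**What to change.** First establish and state whether any 10-week results had been seen when the rule is set.

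- **If none had been seen:** state a fixed sequence, each step at two-sided 0.05, with the full-sample test before the subgroup test and the subgroup test confirmatory only if the preceding steps succeed. Give the immediate-vs-delayed test an explicit place in the sequence, reconciled with the protocol's sample size section; do not make it secondary by default. Alternatively, split alpha across all tests that count as primary: 0.025 each for two, or 0.0167 each for three.
- **If results were already known:** an order or split chosen then does not control the error. Report all primary results together with their 95% confidence intervals (the SAP already plans the intervals), state that multiplicity was not controlled, and do not present a subgroup-only success as a confirmed primary result.

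The cost is one or two sentences in the SAP or report, with no new test and no new data. Under a sequence, later tests lose confirmatory status if an earlier one fails. Under a split, 80% power falls to about 71% at 0.025 or 66% at 0.0167. Under disclosure, a confirmatory subgroup claim is given up.

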Demographic variables. Child's age (in years), sex (male or female), ethnicity (American Indian/Alaskan Native, Hispanic, White, Black/African American, Native Hawaiian/Pacific Islander or Two or more), grade level and school membership were collected by the school district. Height and weight were collected at each school during the school day by a community outreach coordinator trained in research quality measurements, supported by the school nurse and volunteers. Children were asked to take shoes and jackets off and items out of their pockets. Height to the nearest quarter inch was measured twice with a Charder HM200P Portstad Portable Stadiometer. Weight was measured to the nearest 0.1 pounds with a Health O Meter 752KL Heavy Duty Remote Display Digital Scale. Children's first weight status was considered their baseline, with $\leq 5^{\text{th}}$ BMI percentile for their age and sex considered underweight, 5^{th} to 85^{th} percentile healthy weight, $\geq 85^{\text{th}}$ percentile overweight and $\geq 95^{\text{th}}$ percentile as having obesity

Behavioral constructs. Health behavior constructs (13 questions) aligned with Social Cognitive Theory were assessed. Key constructs include self-efficacy ("I think I can be physically active even if it is hot or cold outside."), social norms (example: "My friends think that doing physical activity is fun"), and access or barriers to participation in physical activity and summer programs ("There are lots of places near where I live where I can do physical activities").

Reported activity and sedentary behaviors. A total of 8 questions ask about participation in the VERB program, types of activity in the past 7 days and participation in other summer programs. The number of activities reported were counted and compared before and after the intervention.

Recruitment:

Children were recruited directly at each school by research staff in collaboration with school physical education or health and wellness instructors. Recruitment occurred by providing flyers and tables at school events and drop-off/pick up. Parents were provided with a consent form and children with an assent form explaining the risks and benefits. English and Spanish versions were available. Upon completion of both forms, participants were measured and surveyed (see measurements below).

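### The second primary analysis selects children on a high baseline BMI percentile and tests change from that same reading against zero, so regression to the mean and summer drift cannot be separated from a programme effect.

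*SAP*

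**What the plan says.** The SAP names two primary analyses. In the second, "we will test whether the BMI Percentile from baseline to 10-weeks was significantly different from zero among the highest-risk children"; these are children whose baseline percentile is at or above the 85th, and "GEE models will be used restricting the sample to children with overweight at baseline". The SAP's general paragraph adds that "a significance level of $p=0.05$ will be used to test hypotheses".

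The protocol (Measures, Demographic variables) says a child's "first weight status was considered their baseline". It describes no separate screening measurement.

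For the first primary analysis, the SAP also compares immediate with delayed intervention "by including a variable denoting immediate vs delayed group membership". It does not say whether that variable enters the second model.

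The protocol's Background reports that local children "were much more likely to worsen their weight-related health status during the summer than during the schoolyear". Neither document mentions regression to the mean, or how zero change should be read against that summer trend.

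**The concern.** Zero is the right reference only if these children would not change without the programme. Two forces make that unlikely.

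- **Selection.** Children chosen because one reading was high will on average read lower at the next one. The percentile scale adds to this: it is bounded at 100, so near the top an upward move counts for less than an equal downward move.
- **Summer trend.** By the protocol's own account, untreated local children tend to worsen over these months, which pushes the change upward.

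A significant decrease could be regression to the mean. A null result or an increase could be summer drift hiding a benefit. This is a designated primary analysis in the children the trial regards as most at risk, and none of these results could be read as a programme effect.

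**Working it through.** **The plan's own figure.** The plan gives no power or error rate for this subset. The only related figure is in the protocol's Sample Size calculations: at least 80% power between arms with 80 retained per arm at d = 0.3, two-sided 5%. The retention step reproduces (80/120 = 67%). The power does not: it comes to about 47%. That is a separate matter, and nothing below depends on it.

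**Inputs from the documents**
- Cut-off: 85th percentile, z = 1.036 (SAP).
- Retained children: 2 x 80 = 160 (Sample Size calculations).
- Share at or above the cut-off: 35% (local 11-year-olds) or 50% (Hispanic and Native 5th graders), both from Background. This gives 0.35 x 160 = 56 or 0.50 x 160 = 80 children.
- SD of BMI change: 0.80 to 1.00, per academic year. The protocol's wording is "for each academic year, the average BMI change ranges from 0.35 to 0.55 units", so these are not 10-week figures.

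**Inputs assumed**
- Correlation r between baseline and 10-week BMI z-score. With equal spread at both times, r = 1 - s²/(2S²), where s is the SD of change and S an assumed cross-sectional BMI SD of 3 to 4.
  - Academic-year s: 1 - 1.00²/(2 x 3²) = 0.944, and 1 - 0.80²/(2 x 4²) = 0.980.
  - If change variance grows with time and 10 weeks is a quarter of that interval: 1 - 0.25/18 = 0.986, and 1 - 0.16/32 = 0.995.
  - Measurement error does not shrink with time, so the truth may lie between. Raw-BMI SDs stand in for a z-score correlation.
- Untreated summer drift: 0, +0.05 or +0.10 z.

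**Model, with no programme effect.** Baseline z1 ~ N(μ, 1), with μ set to give the 35% or 50% share. At 10 weeks, z2 = μ + r(z1 - μ) + √(1 - r²)·e + drift. Percentile = 100·Φ(z). Keep z1 ≥ 1.036 and test the mean percentile change against zero with a two-sided 5% t-test, so 2.5% is nominal in each direction (20,000 replicates).

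**Results, 35% share, n = 56**

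| r | Mean change, no drift (percentile points) | False decrease, no drift | False decrease, +0.05 z | False increase, +0.05 z | Drift that cancels the bias (z) |
|---|---|---|---|---|---|
| 0.94 | -1.5 | 58% | 22% | 0.1% | 0.126 |
| 0.96 | -1.0 | 42% | 8% | 0.5% | 0.085 |
| 0.98 | -0.5 | 24% | 0.9% | 6% | 0.043 |
| 0.99 | -0.25 | 14% | 0% | 26% | 0.022 |
| 0.995 | -0.12 | 9% | 0% | 70% | 0.011 |

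With a 50% share (n = 80) and no drift, false decreases are 57%, 42%, 23%, 14% and 9%. At +0.10 z and r = 0.98 (n = 56), 46% of trials show a false increase.

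**Two checks**
- The same test without selection and without drift gives significant decreases in about 2.4% to 2.9% of trials. In this model the excess therefore comes from selection.
- Comparing immediate with delayed in the same selected children, 1:1 and adjusted for baseline percentile, rejects in 4.6% to 5.2% of trials (nominal 5%) in all 30 scenarios: two shares, five values of r, three drifts.

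GEE, clustering and covariates other than baseline percentile were not simulated.

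**The case against.** The strongest reply has five parts.

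1. **Cause.** If change is pure added noise (z2 = z1 + noise), with no regression to the mean, the selected children still show -0.94 points (24% false decreases) at r = 0.94 and -0.16 (7%) at r = 0.99. On that reading about 63% (0.94/1.50) of the bias is curvature of the percentile scale. It stands that the figures combine both effects. But that model lets the spread of BMI widen over 10 weeks, whereas under stable spread the test is near nominal without selection. On the z scale, which has no curvature, false decreases under stable spread are still 28%, 19%, 12%, 8% and 6%.
2. **Size.** The 58% and 42% figures apply roughly a full academic year's spread to 10 weeks, and the protocol describes careful measurement. This stands: r of about 0.986 to 0.995 may be nearer the truth, with a shift of only a few tenths of a point or less. But a high r makes the test more sensitive to drift, as the last rows of the table show.
3. **Direction.** The documents' only directional evidence is upward. Agreed; no net direction is claimed.
4. **The group variable may carry over.** The second paragraph is abbreviated, omitting age, sex and ethnicity too, so the same model on a subset is a natural reading. The arm contrast would then be available, but the stated hypothesis would still be change from zero.
5. **Not unique.** The SAP's other analyses also test against zero, and drift affects the other 10-week BMI test too. Selection on the outcome's own baseline is peculiar to this one.

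**Conclusion.** The concern holds. One reading both selects the children and anchors a primary test against zero, and the protocol itself reports a trend that makes zero an unlikely value without the programme. Followed as written, the analysis gives a result that cannot be attributed to the programme, whichever way it comes out.

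The structural point rests on the documents alone. The size does not: it depends on assumed values of r and drift. Over r = 0.94 to 0.995 with no drift, false decreases run from 58% down to 9% (n = 56), against 2.5%. A drift of only 0.011 to 0.126 z cancels the bias, and more reverses it, so the sign of the net bias is not established. Because this is a primary analysis, it should be corrected before the result is interpreted.

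**What to change.** - Make the tested hypothesis the immediate-versus-delayed difference in 10-week BMI percentile among children at or above the 85th percentile at baseline. Adjust for baseline percentile, age, sex and ethnicity, and measure both arms over the same 10 weeks.
- Alternatively, fit the full-sample model with a group by baseline-stratum term and report the arm difference in the upper stratum.
- Label the pre-post change in this subset descriptive, and state that it is subject to regression to the mean and summer trend.
- State how children were allocated to immediate or delayed intervention.

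**Cost.** SAP wording and model terms. No new data are needed provided the delayed arm was measured, still untreated, over the same 10 weeks. The SAP's existing group comparison on 10-week change implies that measurement, but neither document says so outright. If such data do not exist, the descriptive label is the minimum.

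The interval will be wider and power low. At the protocol's d = 0.3, 28 per arm (56/2) give about 20% power and 40 per arm (80/2) about 26%; 80% power needs d of about 0.76 or 0.63. These figures precede baseline adjustment, which helps, and clustering, which hurts. The contrast also relies on comparable arms, and neither document describes the allocation.

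### The 1-year BMI percentile analysis omits the immediate-versus-delayed group variable, so its test of change against zero cannot separate a programme effect from background trend

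*SAP*

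**What the plan says.** The SAP's primary analysis (baseline to 10 weeks) has two parts. Change in BMI percentile is tested against zero with adjustment for age, sex and ethnicity, and the two groups are then compared "by including a variable denoting immediate vs delayed group membership".

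For the first secondary analysis the SAP says: "we propose to test the difference in Body Mass Index Percentile-score from Baseline to 1-year follow-up using GEE models". This keeps the same linear GEE, the same three adjustment terms and the same test against zero, but has no sentence on group. Its null hypothesis concerns change alone: "We will test the null hypothesis that participants in the intervention did not significantly change their BMI Percentile-score". It names no comparator and no external reference trend.

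On background trend, the Protocol's Background section reports that locally, in 2015, "approximately 20% of 7 year-olds are overweight or obese, but 35% of 11-year olds". It adds that "children in our school district were much more likely to worsen their weight-related health status during the summer than during the schoolyear". The Protocol's sample size section plans for a difference between arms, and its worked example has BMI rising in both groups, by 0.5 and by 0.2 units.

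**The concern.** A test against zero measures a programme effect only if zero is what would have happened without the programme. The Protocol gives reason to doubt that. Overweight is defined by a percentile cut-off, so the 20% and 35% figures are already on the age-standardised scale of the endpoint, and ordinary growth does not explain the difference. Age as a covariate does not remove the problem: it adjusts for differences between children of different ages, not for one child's drift over a year.

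If percentiles drift upward, a programme that exactly prevented the rise would appear as no change, and one that did nothing could appear as a worsening. At stake is the plan's only analysis of whether any effect lasts to 1 year.

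**Working it through.** **Plan's own figure.** The documents give no power or effect size for the 1-year test. The one power statement is for a contrast between arms: d = 0.3, 80 analysed per arm, two-sided 0.05, at least 80%. The normal approximation gives Φ(0.3/√(2/80) − 1.96) = Φ(1.897 − 1.960) = 0.475, so it does not reproduce. That is a separate matter. I take from it only the analysed number, 2 × 80 = 160.

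**Step 1: background drift in percentile points.** Inputs are the Protocol's 20% at age 7 and 35% at age 11, and the 85th-percentile cut-off. Assumptions: z-scores are normal with SD s, the two age groups can be read as one cohort followed over 4 years, and the rise is linear.

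- Mean z at age 7 = 1.036 − s × 0.842; at age 11 = 1.036 − s × 0.385.
- Mean percentile = 100 × Φ(mean z / √(1 + s²)).
- s = 1.0: mean z goes from 0.195 to 0.651 (0.114 a year); mean percentile from 55.5 to 67.7, about 3.1 points a year.
- s = 1.2: mean z goes from 0.026 to 0.574 (0.137 a year); mean percentile from 50.7 to 64.3, about 3.4 points a year.

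I carry forward 3.0 points, the lower end rounded down.

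**Step 2: the test against zero when the programme has no effect.** With n = 160, the rejection probability is about Φ(3.0 × √160 / SD − 1.96). The documents give no SD for 1-year change in percentile, so a range is assumed. The last column replaces 160 by 160/2 = 80, an illustrative design effect of 2 for school and family clustering.

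| Assumed SD (points) | 3.0 × √160 / SD | Rejection probability | With design effect 2 |
|---|---|---|---|
| 5 | 7.59 | 1.00 | 1.00 |
| 10 | 3.79 | 0.97 | 0.77 |
| 15 | 2.53 | 0.72 | 0.43 |
| 20 | 1.90 | 0.48 | 0.27 |

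The nominal rate is 0.05.

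**Step 3: the reverse error.** If the programme exactly cancels the drift, mean change is zero and the test rejects only 5% of the time, although the benefit is 3 points. The Protocol's own example of a useful effect shows the same logic on raw BMI. A treated group rising by 0.2 (SD 1.0, n = 80) gives 0.2 × √80 = 1.79. The chance of a significant increase is then Φ(1.79 − 1.96) = 0.43, and of a significant decrease below 0.001.

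**Step 4: precision of a group contrast.** Its standard error is SD × √(2/80), twice the one-sample SD/√160. If one group is untreated and the effect is 3.0 points, power is about 0.97, 0.48, 0.24 and 0.16 at SDs of 5, 10, 15 and 20, before any allowance for clustering.

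**The case against.** The strongest reply is that the drift is inferred, not documented. The 20% and 35% figures compare different children in a single year and cover ages 7 to 11, while the study enrols ages 5 to 13. The Protocol's BMI gain of 0.35 to 0.55 units per academic year is raw BMI and does not by itself show that age-standardised percentile rises. This stands: the figures suggest a rise but do not establish one, and its size depends on the assumptions in Step 1.

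Four stronger readings are tempting, and the documents do not support them.

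- A reader might infer that the analysis can show nothing about the programme. If the background rises, the test is biased against the programme, so a significant fall would be suggestive of benefit, though still uncontrolled.
- A reader might infer that an ineffective programme would almost certainly be reported as harmful. That needs an SD of about 10 points or less and no clustering.
- A reader might infer that the drift exceeds the planned effect. An effect of d = 0.3 is 2.1 points at SD 7, but 3.0 at SD 10 and 4.5 at SD 15.
- A reader might infer that pooling the groups halves the effect. That requires a delayed group still untreated at 1 year, both groups analysed together and equal numbers. The documents do not say when the delayed group receives the programme, and the SAP's null refers to participants in the intervention without saying that the groups are pooled. If only programme recipients are analysed, there is still no comparator.

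It is also fair to say that restoring the group variable may not recover a treated-versus-untreated comparison. That shapes the fix but does not rescue the test against zero.

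**Conclusion.** The point holds in this form: the 1-year analysis, as written, is a before-after test without the group variable that the SAP uses at 10 weeks. A change from zero cannot be attributed to the programme, and a real benefit may be hidden.

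Under a 3-point drift and no programme effect, the rejection probability runs from about 1.00 down to 0.48 for SDs of 5 to 20 points, and lower with clustering, against 0.05. Those figures rest on the longitudinal reading, normal z-scores and assumed SDs. The attribution problem does not: any non-zero background trend produces it.

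The second primary analysis (children at or above the 85th percentile) and the self-efficacy analysis also omit the group variable, so both likewise lack a comparator. The drift figures above do not apply to self-efficacy.

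**What to change.** In the first secondary analysis, add the immediate-versus-delayed variable and make the group term the test. Add baseline BMI percentile for precision. Report change from zero within each group as descriptive only.

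State in the SAP whether the delayed group had received the programme before the 1-year measurement. If it had, label the contrast as earlier versus later access and draw no controlled efficacy conclusion from it.

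Add the group variable to the second primary and self-efficacy paragraphs and make it the test there too, with the baseline value of the relevant outcome.

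The cost is model terms already available in the data, some SAP wording and the statement on timing. The real downside is precision: before any gain from baseline adjustment, the between-group standard error is twice that of the one-sample test, so a 1-year contrast may well be inconclusive.
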